Ischemic stroke could injure the brain with both neurological dysfunction (including cognitive impairment) and physical disability in patients. It has been shown in the Framingham study that hemiparesis was most common neurological deficit (50%), followed by the cognitive deficits (46.2%), after ischemic brain stroke in elderly. [Kelly-Hayes et al., 2003] In addition, 22.2% to 39.6% patients with ischemic stroke were significantly more disabled from all domains including dependence on activity of daily living, poor health, incontinence, depression, social disability, and need institutionalization. [Kelly-Hayes et al., 2003] In MEDIAS (the Management Effort for Delirium and Insomnia in Acute Ischemic Stroke) study, delirium occurred in 25.8% of acute ischemic stroke patients (i.e., within 7 days after stroke onset) and these delirium patients were older and had significantly worse modified Rankin scale (mRS) scores both at discharge and 1 year after stroke onset. [Matsuzono et al., 2020] Furthermore, these acute ischemic stroke patients with delirium received delirium management including physical restraint alone (45.3%), combined physical restraint and major tranquilizers (36.8%), and major tranquilizers alone (17.8%). The authors raised the concern that physical restraint may be required to ensure patient safety but inversely have potential harmful consequences including death in these acute ischemic stroke patients with delirium. [Matsuzono et al., 2020]

Target-monitored GA to reduce the risk of intraoperative awareness and unfavorable hypotension

The goals of GA are to provide unconsciousness, amnesia, analgesia, and blunting of sympathetic stress responses; however, the incidence of intraoperative awareness during general anesthesia has been estimated to around 0.1-0.2% among general anesthesia. [Myles et al., 2004] Intraoperative awareness can cause significant psychological trauma to the patient which results in

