was in critical situation, uncooperative, or with uncontrolled movement, the anesthesiologist would choose the intubated Sev-GA instead of the scheduled randomization. However, if patient is cooperative and not critical, the patient would be randomly assigned according to the randomization list created with the use of computer-generated, permuted-block sequences. Only the anesthesiologist and physicians involved in EVT are aware of the anesthesia assignment. On the contrary, patients, personnel who collect data, fill out questionnaire and scale measurement, and personnel who assess outcomes are unaware of the group assignments.

The case number is determined according to previous studies. [Ellard et al., 2014; Katznelson et al., 2009; Matsuzono et al., 2020] Under the null hypothesis of there is no mean difference between two groups and no patients lost follow-up. The type I error is set as 0.05 with power of 0.8. A total of 298 patients is required to detect a difference of 12.8% in POCD incidence in acute ischemic stroke patients receiving EVT therapy within 7 days after stroke. Considering the potential 10% attrition rate, a sample size of 328 participants will be recruited into the present clinical trial.

General anesthesia protocol

American Society of Anesthesiologists standard monitors (including pulse oximeter, ECG, and non-invasive blood pressure), invasive arterial blood pressure monitoring, end-tidal agent monitor (including CO₂ and anesthetic concentrations), hypnotic level monitor (either BIS or PSI), and cerebral oximeter using near-infrared spectroscopy are applied to all patients peri-procedurally.

Non-intubated TIVA-propofol group:

With the application of Optiflow nasal high flow set at a flow rate of 20 L/min and 60% FiO₂, total intravenous anesthesia is induced with target-controlled infusion of propofol (effect site (Ce) concentration around 1.5-2 μ g/ml) and remifentanyl (Ce value around 1.0-1.5 ng/ml), and adjusted as required.

Intubated Sev-GA group:

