After preoxygenation for 3 minutes with 100% oxygen, anesthesia is induced with intravenous injection of propofol (1.5-2 mg/kg), remifentanyl infusion (Ce value around 1-1.5 ng/kg), and cisatracurium (0.15-0.2 mg/kg), and followed by endotracheal intubation. General anesthesia is maintained with cisatracurium (0.03 mg/kg every 45-50 min), remifentanyl (Ce value around 1-1.5 ng/kg) and sevoflurane inhalation. Sevoflurane concentration will be adjusted to keep BIS value within the range of 40-60. Mechanical ventilation will be processed at volume-controlled mode with fraction of inspired oxygen (FiO₂) 60%, tidal volume 6 ml/kg, and respiratory rate 9-12/min

to keep normocapnia and avoid desaturation during the EVT procedure.

Peri-EVT procedural anesthetic monitoring

1. Standard monitoring: continuous ECG, non-invasive blood pressure (NIBP), pulse oximeter (SpO₂)
2. Invasive arterial blood pressure (ABP)
3. Anesthetic agent monitor: to monitor sevoflurane concentration
4. Cerebral oximeter (ScO₂): for regional brain oxygenation monitor
5. End-tidal CO₂ (ETCO₂) monitor
6. Processed electroencephalogram (EEG) monitoring: either with Medtronic BIS™ brain monitoring system with bispectral index (BIS) or Masimo SedLine Brain function monitoring with Patient State Index (PSI)

Physiologic target during peri-EVT procedure

1. Propofol target effect-site concentration (Ce): 1.5 ~ 2.0 μ g/ml.
2. Remifentanyl Ce: 1.0 ~ 1.5 ng/ml
3. Partial pressure of arterial blood CO₂ (PaCO₂): kept around 30-40 mmHg
4. ETCO₂: kept around 35-45 mmHg
5. Target-controlled sedation level: PSI maintained between 25 and 50 or BIS maintained between 40 and 60 by adjusting the infusion rate of propofol or the inhaled concentration of sevoflurane
6. Systolic blood pressure (target-controlled): before completion of thrombectomy (110-180 mmHg), and after completion of thrombectomy (110 -140 mmHg).

Post-procedural care

After completion of the EVT procedure, patient will be transferred to the Stroke Care Unit for post-procedural intensive care. The endotracheal tube will be removed once weaning from mechanical ventilation, ability to spontaneous respiration, and recovery of both muscle power and respiratory mechanics.

Outcomes:

Cognitive function and delirium evaluation

Cognitive functions (including delirium) will be assessed pre-procedure (baseline) and emergency department (before EVT), on days 1 and 7 after EVT procedure, using the confusion assessment method (CAM).

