Neurological functional assessment

National Institute of Health Stroke Scale (NIHSS) and modified Rankin scale (mRS) will be assessed before (baseline but after stroke) and after EVT on days 1 and 7 after procedure up to 3 months follow-up.

Data collection and analysis

The primary outcome is to compare the incidence and severity of postoperative delirium between intubated GA-sevoflurane and non-intubated TIVA-propofol, which is assessed using CAM. The secondary outcomes are neurological and clinical outcomes by assessing the NIHSS and mRS, and activity of daily living. All analyses are based on the intention-to-treat principle. The normally distributed data will be expressed as mean \pm SD, while non-normally distributed data will be presented as median and interquartile ranges (IQR). Binary outcomes will be analyzed with logistic regression. The Chi-Square test is used to compare categorical data. The Mann-Whitney test and Kruskal-Wallis test are used to compare non-normally distributed data within the trial. Modified Rankin score is analyzed with an ordinal logistic regression. Safety outcomes are assessed with Chi-Square test for categorical variables and Student's t test for continuous variables. *P* values less than 0.05 are considered statistically significant. All data analysis will be performed using the Statistical Package for the Social Sciences (SPSS) version 17.0 for Windows (SPSS Inc., Chicago, IL, USA).

Questionnaire

1. Modified Rankin Scale: assessed before procedure and the day at discharge, respectively.

Score	Degree of disability or dependence in the daily activities
0	No symptoms
1	No significant disability: able to carry out all usual activities, despite some symptoms
2	Slight disability: able to look after own affairs without assistance, but unable to carry out all previous activities
3	Moderate disability: requires some help, but able to walk unassisted
4	Moderately severe disability: unable to attend to own bodily needs without assistance, and unable to walk unassisted
5	Severe disability: requires constant nursing care and attention, bedridden, incontinent
6	Dead

2. National Institutes of Health Stroke Scale (NIHSS): assessed before procedure and day 1 after EVT, and the day at discharge, respectively.

Time point	Before EVT	D1 after EVT	Day at discharge
------------	---------------	-----------------	---------------------

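### Pre-thrombectomy CAM and NIHSS are recorded but given no role in the analysis, and the plan does not say how delirium already present before EVT counts towards postoperative delirium

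*Combined protocol and SAP*

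**What the plan says.** All references are to the combined protocol and SAP.

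- **Primary outcome** (Data collection and analysis): "The primary outcome is to compare the incidence and severity of postoperative delirium", assessed with CAM. Postoperative is not defined as new-onset.
- **CAM schedule** (Cognitive function and delirium evaluation): CAM "will be assessed pre-procedure (baseline) and emergency department (before EVT), on days 1 and 7 after EVT procedure". The CAM form in the Questionnaire section has a single column before EVT, then day 1, day 7 and discharge.
- **CAM form**: delirium requires feature 1, an acute change from baseline with fluctuation. The form does not say what that baseline is.
- **NIHSS and mRS** (Neurological functional assessment): these "will be assessed before (baseline but after stroke) and after EVT on days 1 and 7 after procedure", with follow-up to 3 months.
- **Exclusions** (Subjects): anaesthetic allergy and refusal only.
- **Analysis** (Data collection and analysis): "Binary outcomes will be analyzed with logistic regression. The Chi-Square test is used to compare categorical data". For the mRS, "Modified Rankin score is analyzed with an ordinal logistic regression". No covariate, stratum or change-from-baseline rule is given for any outcome.
- **Sample size** (Subjects): 298 patients to "detect a difference of 12.8% in POCD incidence in acute ischemic stroke patients receiving EVT therapy within 7 days after stroke", with type I error 0.05 and power 0.8.
- **Background rate** (Cognitive dysfunction after ischemic stroke): in a cited study "delirium occurred in 25.8% of acute ischemic stroke patients (i.e., within 7 days after stroke onset").

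**The concern.** Acute stroke itself causes delirium, so some patients may be CAM-positive before any anaesthetic is given. If such a patient is still CAM-positive on day 1 or 7, the plan does not say whether this is a postoperative event, a patient to set aside, or something the analysis accounts for. As written it can be counted as an event, although the anaesthetic did not start it.

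Pre-EVT CAM is also likely to predict later CAM, and pre-EVT NIHSS to predict later NIHSS and mRS. Leaving both out gives up precision at no saving. Leaving their use open also allows the choice of model to be made after the data are seen.

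**Working it through.** **1. Reproduce the planned size.** Inputs: α = 0.05, power 0.80 and a difference of 12.8 points (Subjects); reference rate 25.8% (background section). Assumed: two-sided test, equal arms, and 25.8% as the higher rate, so the other is 25.8 − 12.8 = 13.0%. With p̄ = (0.258 + 0.130)/2 = 0.194:

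n per arm = [1.96·√(2·p̄(1−p̄)) + 0.8416·√(p₁(1−p₁) + p₂(1−p₂))]² / (p₁−p₂)² = 148.6, i.e. 149 per arm and 298 in total, as stated. Power at 149 per arm is 80.1%.

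**2. Two meanings of the planning rates.** Let b be the prevalence of CAM-positive patients before EVT and s the probability that their delirium is still recorded on day 1 or 7. Neither is in the documents, so both are assumptions. Arms are taken as balanced, with s equal in both. Because "if patient is cooperative and not critical, the patient would be randomly assigned according to the randomization list", the low end of b is the more plausible for randomised patients.

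- *A: rates count all delirium since stroke.* Totals stay at 25.8% and 13.0%. The new-onset rate in CAM-negative patients is (p − b·s)/(1 − b). At b = 5%, s = 90%: (0.258 − 0.045)/0.95 = 22.4% and (0.130 − 0.045)/0.95 = 8.9%.
- *B: rates apply only to CAM-negative patients, and persisting delirium is added.* The total is b·s + (1 − b)·rate. At b = 5%, s = 100%: 0.05 + 0.95 × 0.258 = 29.5% and 0.05 + 0.95 × 0.130 = 17.4%. The difference falls to 0.95 × 12.8 = 12.2 points.

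**3. Power at 149 per arm** (simulation, 100,000 runs; unadjusted Chi-Square / Mantel-Haenszel stratified by pre-EVT CAM):

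| b | s | A | B |
|---|---|---|---|
| 1% | 70% | 80.4 / 81.4 | 79.0 / 79.8 |
| 1% | 90% | 80.6 / 81.9 | 78.5 / 79.8 |
| 3% | 70% | 80.7 / 83.0 | 75.7 / 77.8 |
| 3% | 90% | 80.9 / 84.8 | 74.7 / 78.7 |
| 5% | 70% | 80.6 / 84.3 | 72.7 / 76.1 |
| 5% | 90% | 80.7 / 87.7 | 70.9 / 77.3 |

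Under the null (b = 3% or 5%), rejection rates were 4.8–5.2%. A logistic model with arm and pre-EVT CAM agrees with the stratified test: at b = 5% and s = 70% / 90%, 84.7 / 87.2% under A and 76.1 / 77.0% under B.

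**4. When the gain disappears.** Under A at b = 5% and s = 35%, power is 80.8% unadjusted and 81.2% stratified. With no association between pre-EVT and later CAM it is 80.9% and 80.7%.

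**5. CAM-negative patients only.** By formula under B, n = 149 × 0.95 = 141.6 per arm gives 78.0% at b = 5%. By simulation at b = 5%, s = 70%, this analysis has 87.1% under A (stratified 84.6% in the same runs) and 78.8% under B (stratified 75.9%).

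**6. Follow-up NIHSS.** In a linear model with equal SDs and correlation ρ with pre-EVT NIHSS, variance relative to the raw comparison is 2(1 − ρ) for change and 1 − ρ² when adjusted. At assumed ρ = 0.3 / 0.5 / 0.7 this is 1.40 / 1.00 / 0.60 for change and 0.91 / 0.75 / 0.51 adjusted.

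**The case against.** - **Logistic regression can carry covariates.** This stands. Delirium is binary, and the plan assigns binary outcomes to logistic regression. A reader might infer that an unadjusted Chi-Square is the planned primary test, but the documents do not say so. The gap is that no covariate is named.
- **No power is lost.** This largely stands. A reader might infer from column B that the trial is underpowered, especially since unadjusted power falls to about 61% at 10% prevalence with full persistence. That needs planning rates that apply only to CAM-negative patients. The background rate and the sample-size statement both count from the stroke, which is column A, where there is no shortfall.
- **The CAM baseline is not wholly open.** This stands in part. A reader might infer that feature 1 could be judged from pre-EVT status, so that unchanged delirium would not count. But the form applies the same wording to its pre-EVT column, where pre-EVT status cannot be its own reference. The form therefore points to an earlier reference, though it never states one.
- **The gains depend on chosen inputs.** This stands. High persistence, equal in both arms, places all the treatment effect in CAM-negative patients. With low persistence the gain vanishes (step 4).
- **Stratifying does not stop persisting delirium counting as an event.** This stands. The counting rule has to be written separately, and the CAM-negative analysis deserves prominence, since it was at least as powerful in step 5.

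**Conclusion.** The concern holds as a gap in endpoint definition and pre-specification. Delirium present before EVT is neither excluded nor given a counting rule, and the recorded pre-EVT CAM and NIHSS have no stated use. On the reading the documents favour, the efficiency at stake is modest: about 1–4 points of power at 1–3% prevalence and 4–7 points at 5%, for 70–90% persistence, and close to nothing at about 35%. Only if the planning rates describe CAM-negative patients does unadjusted power fall below plan, from about 79% at 1% prevalence to 71–73% at 5%. Stratification then recovers part of the loss.

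These figures assume balanced arms, equal persistence in both, an inferred 13.0% lower rate, and delirium on day 1 or 7 as the event. They do not show that 298 is wrong. Nor would adjustment repair the assignment of critical or uncooperative patients to sevoflurane outside the randomisation list, which is a separate problem. The NIHSS and mRS point is sound but secondary.

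**What to change.** 1. In Data collection and analysis, state how a patient who is CAM-positive before EVT counts towards postoperative delirium. On the CAM form, state which reference status feature 1 uses. Name the one pre-EVT CAM that serves as baseline, since the text appears to list two and the form has one, and give a rule for a missing one.
2. Pre-specify one primary test of CAM delirium on day 1 or 7 by assigned arm. Use either Mantel-Haenszel stratified by pre-EVT CAM, with the risk difference and 95% CI, or the logistic model with pre-EVT CAM as covariate. The Mantel-Haenszel version stays estimable if all CAM-positive patients are events or none are. Say that the discharge CAM is outside this endpoint, if that is intended.
3. Report new-onset delirium among patients CAM-negative before EVT as a key supporting analysis.
4. Adjust follow-up NIHSS and the ordinal mRS model for pre-EVT NIHSS.

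**Cost:** analysis-plan wording and one line on the form, settled before outcome data are seen; no new data. Any odds ratio reported would be conditional, so the risk difference should lead. Power loss is negligible (about 0.2 points) if pre-EVT CAM is not prognostic. The CAM-negative analysis uses fewer patients and answers a narrower question.

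### Student's t test is fixed for continuous safety variables in arms that are likely to be unequal; if the spreads also differ its error rate is wrong, and Welch's t test avoids this at almost no cost.

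*Combined protocol and SAP*

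**What the plan says.** All references are to the combined protocol and SAP.

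- **Safety tests** (Data collection and analysis): "Safety outcomes are assessed with Chi-Square test for categorical variables and Student's t test for continuous variables". The section gives no rule for unequal variances and none for small expected counts. No safety outcome, event rate or SD is defined anywhere in the document.
- **Non-normal data** (same paragraph): "The Mann-Whitney test and Kruskal-Wallis test are used to compare non-normally distributed data within the trial". The safety sentence comes later and does not repeat this.
- **Significance** (same paragraph): P "values less than 0.05 are considered statistically significant". Sidedness is not stated; I take it as two-sided.
- **Allocation** (Subjects): for critical, uncooperative or moving patients, "the anesthesiologist would choose the intubated Sev-GA instead of the scheduled randomization". No rule moves patients the other way, and neither an arm ratio nor an expected share of diverted patients is given.
- **Size** (Subjects): "A total of 298 patients is required to detect a difference of 12.8% in POCD incidence", and then "Considering the potential 10% attrition rate, a sample size of 328 participants will be recruited".

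**The concern.** Student's t pools the two variances. The pooled estimate gives the correct standard error when the arms have equal size or equal spread, and it fails when both differ. One-way diversion makes unequal size likely. Equal spread cannot be presumed either: one arm is ventilated to set targets and the other is not intubated, which could widen the TIVA spread in respiratory values, while placing critical patients in Sev-GA could widen the spread there.

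The plan sets out to find a safe anesthetic regimen and judges by P below 0.05. If the smaller arm has the larger SD, a difference in safety is declared too often. If the larger arm has the larger SD, a real difference is too easily missed.

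**Working it through.** **1. The plan's own figure.** The plan gives no figure for the safety tests, so the check is on the total of 298. Its sample-size text states "The type I error is set as 0.05 with power of 0.8". I assume that the reference rate is the one in the background ("delirium occurred in 25.8% of acute ischemic stroke patients"), so the rates are 25.8% and 25.8 − 12.8 = 13.0%, with mean 19.4%:

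n per arm = [1.96·√(2·0.194·0.806) + 0.842·√(0.258·0.742 + 0.130·0.870)]² / 0.128² = 148.6, rounded up to 149.

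Two arms give 298, and 298 × 1.10 = 327.8, or 328. The figure reproduces with equal arms.

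**2. Arm sizes (assumed).** If listed patients split 1:1 and diverted patients count within the 328 as Sev-GA, then diverted = 328 − 2 × TIVA:

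- 131/197 (TIVA/Sev-GA): 66 diverted (20%)
- 110/218: 108 diverted (33%)
- 66/262: 196 diverted (60%)

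**3. Student's t.** With n and σ for TIVA (T) and Sev-GA (S), and N = 328:

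- pooled variance s² = [(n_T − 1)σ_T² + (n_S − 1)σ_S²] / (N − 2)
- assumed variance of the difference A = s²(1/n_T + 1/n_S)
- true variance B = σ_T²/n_T + σ_S²/n_S
- large-sample type I error = 2[1 − Φ(1.96·√(A/B))]

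*110/218, TIVA SD double.* s² = (109·4 + 217·1)/326 = 2.003; A = 0.02740; B = 4/110 + 1/218 = 0.04095; √(A/B) = 0.818; error = 10.9%.

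*110/218, Sev-GA SD double.* s² = (109·1 + 217·4)/326 = 2.997; A = 0.04099; B = 1/110 + 4/218 = 0.02744; √(A/B) = 1.222; error = 1.7% (1.6% at 109/219).

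| TIVA/Sev-GA | Equal SDs | TIVA SD double | Sev-GA SD double |
|---|---|---|---|
| 164/164 | 5.0% | 5.0% | 5.0% |
| 131/197 | 5.0% | 8.3% | 2.7% |
| 110/218 | 5.0% | 10.9% | 1.7% |
| 82/246 | 5.0% | 15.1% | 0.8% |

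With an SD ratio of 1.5 at about 2:1, the error is 8.5% (TIVA larger) or 2.6% (Sev-GA larger). In simulations of 20,000 trials per scenario, with arms up to 3:1, Welch's t stayed between 4.7% and 5.3%.

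**4. Chi-Square.** Exact size is the sum, over all event pairs with P < 0.05, of the product of the two binomial probabilities at a common event rate.

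- Smallest expected count at least 5: 4.6% to 5.2% at every ratio from 1:1 to 4:1.
- Event rates up to 2%, arms from 1:1 to 2:1: 0.1% to 4.8%.
- 66/262: 9.2% at a 0.5% event rate and 7.1% at 1%. Fisher's exact test gives 1.3% and 1.8%.
- 110/218 at a 1% rate: Chi-Square 4.14% against TIVA plus 0.06% against Sev-GA, 4.2% in total. Fisher: 1.86% plus 0.013%, 1.9% in total.

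**The case against.** The strongest reply is that unequal arms break neither test. This stands: with equal SDs Student's t is at 5.0% at every ratio, and with adequate expected counts Chi-Square is close to 5%. A reader might infer that the allocation rule alone gives both tests the wrong error rate. The documents do not support that.

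Second, the inputs are assumed. This also stands. The document gives no SD, event rate or arm ratio. It lists oxygen saturation and end-tidal CO₂ as monitoring, not as safety endpoints.

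Third, the arms may not be unequal. All analyses are to follow intention-to-treat. If that means the scheduled allocation, the arms could stay near 1:1 and the t-test problem largely disappears. The plan does not say how diverted patients are analysed, so this remains open.

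Fourth, the general Mann-Whitney sentence arguably covers non-normal safety data already. That is a fair reading, so I do not claim that skewed data are forced into a t test. Normal data with unequal spread remain uncovered.

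Finally, a reader might infer that the safety comparison leans against TIVA and that Fisher's test would cure it. For continuous variables the direction is unknown. For rare events the asymmetry comes from arm size and discreteness, and Fisher's test has it too.

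**Conclusion.** The point holds for Student's t, conditionally. If patients are analysed as assigned, Sev-GA is likely to be the larger arm. If the SDs then differ, the test does not hold its level: about 11% or about 1.6% to 1.7% at roughly 2:1 with a twofold SD ratio, depending on which arm varies more. These figures rest on assumed arm sizes and SD ratios. Because Welch's t holds near 5% throughout, the change is worth making without settling those assumptions.

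The Chi-Square part is secondary. Clear inflation (7% to 9%) appears only near 4:1 with event rates of about 1% or less; for rare events at 1:1 to 2:1 the test is at or below 5%.

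No choice of test repairs the confounding that arises when critical patients are diverted to Sev-GA. That is a separate and larger problem.

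**What to change.** Replace the safety sentence with wording such as:

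> Continuous safety variables are compared with Welch's unequal-variance t test, or with the Mann-Whitney test if non-normal. Categorical safety variables are compared with the Chi-Square test, or with an exact test when any expected count is below 5. Every comparison is reported with the estimated difference and its 95% confidence interval.

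Add one sentence saying whether diverted patients are analysed in the arm they received or the arm the list scheduled.

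The cost is a short text change. Welch's t has practically no statistical cost and is standard output in the named software. Fisher's exact test is conservative and loses some power for rare harms, without removing the asymmetry between arms; the confidence intervals help to keep rare-harm signals visible.

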Endovascular thrombectomy (EVT) for acute ischemic stroke with large vessel occlusion

The time elapsed since onset of symptoms of stroke (time window) play important roles in clinical outcome of the acute ischemic stroke. In 2015, the encouraging results of the MR CLEAN (Multicenter Randomized Clinical Trial of Endovascular Treatment for Acute Ischemic Stroke), ESCAPE (Endovascular Treatment for Small Core and Anterior Circulation Proximal Occlusion with Emphasis on Minimizing CT to Recanalization Times), EXTEND-IA (Extending the Time for Thrombolysis in Emergency Neurological Deficits-Intraarterial), and SWIFT PRIME (Solitaire with the Intention for Thrombectomy as Primary Endovascular Treatment) trials all demonstrated the superiority of intra-arterial EVT therapy over intravenous tissue plasminogen activator (IV-tPA) alone in patients with acute ischemic stroke due to large vessel occlusion in the anterior circulation. [Berkhemer et al., 2015; Campbell et al., 2015; Goyal et al., 2015; Saver et al., 2015] Therefore, the American Heart Association/American Stroke Association (AHA/ASA) published the updated guidelines on EVT for the early management of patients with acute ischemic stroke in 2018 [Powers et al., 2018; Tang et al., 2019]. The criteria (Class I; Level of Evidence A) for EVT therapy in patients of acute ischemic stroke include (1) age ≥ 18 years, (1) pre-stroke functionally independent with modified Rankin Scale (mRS) score of 0 to 1 and have post-stroke neurological deficit assessed with a National Institute of Health Stroke Scale (NIHSS) score ≥ 6 , (3) causative occlusion of the internal carotid artery or proximal middle cerebral artery (MCA-M1 branch), (4) the volume of the ischemic core estimated with the Alberta Stroke Program Early CT score (ASPECTS) is not large and should be ≥ 6 , and (5) the treatment can be initiated (time to groin puncture) within 6 hours of symptom onset. In addition, EVT should be offered regardless of whether the patient received IV-tPA therapy. [Powers et al., 2018]

Anesthesia for EVT

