	
position for the full 5 seconds
 
1: Drift; the leg drifts to an intermediate position prior to the end of the full 5 seconds, but at no point touches the bed for support
 
2: Limited effort against gravity; the leg is able to obtain the starting position, but drifts down from the initial position to physical support prior to the end of the 5 seconds
 
3: No effort against gravity; the leg falls immediately after being helped to the initial position, however, the patient is able to move the leg in some form (e.g. hip flex)
 
4: No movement; patient has no ability to enact voluntary movement in this leg
	
Right
 
(6b)
			

7. Limb ataxia
	
0: Normal coordination; smooth and accurate movement
 
1: Ataxia present in 1 limb; rigid and inaccurate movement in one limb
 
2: Ataxia present in 2 or more limbs: rigid and inaccurate movement in both limbs on one side
				

8. Sensory	0: No evidence of sensory loss 1: Mild-to-Moderate sensory loss; patient feels the pinprick, however he or she feels as if it is duller on one side 2: Severe to total sensory loss on one side; patient is not aware he or she is being touched in all unilateral extremities			
9. Language	0: Normal; no obvious speech deficit 1: Mild-to-moderate aphasia; detectable loss in fluency, however, the examiner should still be able to extract information from patient's speech 2: Severe aphasia; all speech is fragmented, and examiner is unable to extract the figure's content from the patient's speech. 3: Unable to speak or understand speech			
10. Speech	0: Normal; clear and smooth speech 1: Mild-to-moderate dysarthria; some slurring of speech, however the patient can be understood 2: Severe dysarthria; speech is so slurred that he or she cannot be understood, or patients that cannot produce any speech			
11. Extinction and Inattention	0: Normal; patient correctly answers all questions 1: Inattention on one side in one modality; visual, tactile, auditory, or spatial 2: Hemi-inattention; does not recognize stimuli in more than one modality on the same side			
Scores (0-42)				

6. Confusion Assessment Method (CAM): assessed before procedure and day 1 and 7 after EVT, and the day at discharge, respectively.

Confusion Assessment Method (CAM)	Date of Assessment	Before EVT	D1 after EVT	D7 after EVT	Day at discharge
-----------------------------------	--------------------	------------	--------------	--------------	------------------

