Diagnostic Algorithm	Time of Assessment				
		Yes or No	Yes or No	Yes or No	Yes or No
1. Acute onset and fluctuating course? (Acute change in mental status from baseline, fluctuating behavior through the day)					
2. Inattention? (Difficulty focusing attention, easily distracted, difficulty keeping track of what is being said)					
3. Disorganized thinking? (disorganized or incoherent thinking, rambling or irrelevant conversation, unclear or illogical flow of ideas)					
4. Altered level of consciousness? (This feature is shown by any answer other than "alert", including: hyper-alert, lethargic, stupor, or coma)					
The diagnosis of Delirium by CAM requires the presence of features 1 and 2 AND EITHER 3 or 4					
Delirium detected		Yes No (Circle)	Yes No (Circle)	Yes No (Circle)	Yes No (Circle)

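### The CAM form that defines the primary outcome has no rule for aphasic patients, whom the entry criteria admit, so aphasia may be misread as delirium

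*Combined protocol and SAP*

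**What the plan says.** **Who enters.** The Subjects section ties eligibility to the stroke guidelines. The EVT background section lists the 2018 guideline criteria, among them NIHSS of at least 6 and "causative occlusion of the internal carotid artery or proximal middle cerebral artery (MCA-M1 branch". The only exclusions are allergy to the study anesthetics and refusal.

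**The outcome.** Data collection and analysis makes the incidence and severity of delirium by CAM the primary outcome and assigns binary outcomes to logistic regression. No covariates are named.

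**The form.** In Questionnaire item 6, a delirium diagnosis needs features 1 and 2 plus either 3 or 4.
- Feature 1 combines acute change from baseline and fluctuation over the day in one Yes/No box.
- Feature 2 is "Difficulty focusing attention, easily distracted, difficulty keeping track of what is being said".
- Feature 3 is "disorganized or incoherent thinking, rambling or irrelevant conversation, unclear or illogical flow of ideas".

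The form has no instruction for aphasic patients and no entry for a patient who cannot be assessed.

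**Language is recorded elsewhere.** NIHSS item 9 (Questionnaire item 2) grades language from 0 to 3. Score 1 is already mild-to-moderate aphasia, and score 2 is "Severe aphasia; all speech is fragmented, and examiner is unable to extract the figure's content from the patient's speech". Nothing links this item to the CAM. The NIHSS form has columns for before EVT, day 1 and discharge. The CAM form also has day 7, and the Neurological functional assessment section plans a day 7 NIHSS.

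**The concern.** Features 2 and 3 are judged largely through conversation. A patient who is awake and not delirious but has a language deficit can appear to lose the thread of what is said and to produce irrelevant speech. Whether that patient is called delirious then depends on feature 1, and the form protects that step weakly:

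- Acute change and fluctuation share one box, so the record cannot show which was credited.
- Each assessment has one time entry, and the plan does not say how a rater establishes fluctuation over a day.
- The baseline for the CAM is unclear. The Outcomes section lists a pre-procedure baseline and an emergency department assessment, whereas the NIHSS and mRS baseline is explicitly after the stroke. Against a pre-stroke baseline, a new aphasia can look like acute change.

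At stake is the specificity of the primary outcome. The plan hypothesizes no significant difference between the anesthetics, so a null result would be hard to interpret if measurement error contributed to it. A positive result would be equally hard to interpret if the error differed between arms.

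**Working it through.** **Inputs from the plan** (sample size paragraph in Materials and methods): alpha 0.05, target power 80%, and "A total of 298 patients is required to detect a difference of 12.8% in POCD incidence in acute ischemic stroke patients". The background section reports that "delirium occurred in 25.8% of acute ischemic stroke patients (i.e., within 7 days after stroke onset".

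**Assumptions:** two-sided test and 1:1 allocation (neither is stated); planning rates of 25.8% and 13.0% (25.8 − 12.8), inferred because they reproduce the plan's total.

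**Step 1. Reproduce 298.** With d = 0.128 and mean rate 0.194, the pooled two-proportion formula is

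n = [1.960·√(2·0.194·0.806) + 0.842·√(0.258·0.742 + 0.130·0.870)]² / 0.128² = (1.096 + 0.464)² / 0.01638 ≈ 148.6, so 149 per arm, 298 in total.

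This matches exactly. Power at 149 per arm is 0.801.

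**Step 2. Equal false positives.** Let f be the fraction of non-delirious patients rated CAM-positive because of aphasia. The documents give no value, so f is an assumption. No true delirium is taken to be missed. The observed rate is p + f(1 − p), and the observed difference is (1 − f) times the true one. For f = 10%: 0.258 + 0.10·0.742 = 0.332 and 0.130 + 0.10·0.870 = 0.217.

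| f, both arms | Observed rates | Difference (points) | Power, 149 per arm | Total N for 80% power |
|---|---|---|---|---|
| 0 | 25.8% vs 13.0% | 12.8 | 0.80 | 298 |
| 5% | 29.5% vs 17.4% | 12.2 | 0.70 | 380 |
| 10% | 33.2% vs 21.7% | 11.5 | 0.61 | 470 |
| 20% | 40.6% vs 30.4% | 10.2 | 0.46 | 684 |

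**Step 3. Unequal false positives, no true effect.** The spurious difference is (f in Sev-GA − f in TIVA)·(1 − p). For 15% vs 5% at p = 13%: 0.10·0.87 = 8.7 points. The last two columns give the spurious difference and the chance of rejecting at 149 per arm.

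| f, Sev-GA vs TIVA | True rate 13.0% in both arms | True rate 25.8% in both arms |
|---|---|---|
| 10% vs 5% | 4.4 points; 16% | 3.7 points; 10% |
| 15% vs 5% | 8.7 points; 45% | 7.4 points; 27% |
| 20% vs 5% | 13.1 points; 76% | 11.1 points; 52% |

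Unequal error is possible because, under Subjects, critical, uncooperative or uncontrollably moving patients receive Sev-GA instead of their randomized assignment. That these patients have more language deficit is an inference, not something the plan states.

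**The case against.** The strongest objection is that feature 1 is mandatory and asks for fluctuation. A fixed aphasia does not fluctuate, so as worded it fails the algorithm. This stands. A reader might infer that the outcome necessarily counts focal stroke signs as delirium, but the form does not say so: a false positive needs a rater to misapply feature 1 or to guess in an untestable patient. What remains is a risk that the form does little to prevent or reveal.

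A reader might extend the point to neglect. The documents do not support that. Feature 2 describes general distractibility, not one-sided inattention, and an alert patient with neglect and intact speech meets neither feature 3 nor feature 4.

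A reader might also infer that the error can only dilute a difference. That requires equal error in both arms, which the non-random route to Sev-GA leaves in doubt.

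The CAM is also done before EVT, and a deficit that triggers it might already show there. That is fair, but the analysis section gives no rule for using that assessment, so it does not protect the outcome as the plan stands.

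Finally, 25.8% is an observed delirium rate in acute ischemic stroke and may already contain some of this misclassification. Adding f on top could then double-count, so the power figures are illustrative.

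**Conclusion.** The point holds as a risk of misclassification from aphasia. The entry criteria admit aphasic patients, two CAM features can be met by a language deficit, the form has neither a scoring rule nor an unable-to-assess entry, and the analysis does not use the language score recorded before EVT.

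The size cannot be fixed from the documents. Under assumed equal false-positive fractions of 5% to 20%, power falls from 0.80 to between 0.70 and 0.46. Under the assumed unequal fractions, a spurious difference of about 4 to 13 points appears. Both sets of figures rest on the inferred rates of 25.8% and 13.0% (or one of them common to both arms), 149 per arm, a two-sided test, no missed delirium, and values of f that have no source in the plan. They show which way the error acts and how sensitive the design is to it; they do not estimate what will happen.

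**What to change.** 1. **Adjust the primary delirium logistic regression for the pre-EVT NIHSS item 9 score.** It is already collected before treatment. Adjustment addresses imbalance in language deficit between arms; it does not remove individual misclassification or the other effects of non-random assignment.
2. **Pre-specify a sensitivity analysis in patients whose pre-EVT language score is 0.** A 0–1 cut would not serve, because score 1 is already aphasia. State that this subset has lower power.
3. **Clarify the CAM form.** Feature 1 is Yes only when acute change and fluctuation are both present, so stable aphasia alone does not qualify. Add an unable-to-assess option, report its use by arm, and state how these patients enter the analysis.
4. **Add the day 7 column to the NIHSS form**, in line with the day 7 assessment already planned, so that language is recorded beside the day 7 CAM.

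**Cost:** one covariate, one extra analysis, two edits to the CAM form and one column on the NIHSS form. Treatment and sample size do not change. The main downside is that some severely aphasic patients will be recorded as unassessable, which reduces the number with a usable primary outcome.
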